Appendix Table 2. PK and Anti-Drug Antibody Sampling

With the implementation of Amendment 4, PK samples are no longer being collected and subjects are past Week 16.

Study Day	Study Week	BI 836826 PK	ADA analysis	Idelalisib PK
8	2	Before start of BI 836826 drug infusion	Before start of BI 836826 drug infusion	Within 30 min prior to idelalisib dose
		Shortly before end of infusion		1.5 hr after idelalisib dose
9	2	Before start of BI 836826 drug infusion		
		Shortly before end of infusion		
15	3	Before start of BI 836826 drug infusion		
		Shortly before end of infusion		
22	4	Before start of BI 836826 drug infusion		Within 30 min prior to idelalisib dose
		Shortly before end of infusion		1.5 hr after idelalisib dose
23	4	8-10 hr after start of drug infusion		
[25-27]		23-25 hr after start of drug infusion		
36 to 106	6 through 16	72-120 hr after start of drug infusion		
		Before start of BI 836826 drug infusion	Weeks 6, 10, and 14 Before start of BI 836826 drug infusion	Weeks 6 and 14: within 30 min prior to, and 1.5 hr after idelalisib dose
	18	Shortly before end of infusion (Weeks 6, 10, and 14 only)		
			Before start of BI 836826 drug infusion	
120				
176 to 316	26 through 46		Weeks 26, 34, and 42 Before start of BI 836826 drug infusion	
344	30d follow up/EOS		At any time during the visit	

Appendix 3. ECOG Performance Status Scoring System

Grade	ECOG
0	Fully active, able to carry on all pre-disease performance without restriction
1	Restricted in physically strenuous activity but ambulatory and able to carry out work of a light or sedentary nature, eg, light house work, office work
2	Ambulatory and capable of all self-care but unable to carry out any work activities. Up and about more than 50% of waking hours
3	Capable of only limited self-care, confined to bed or chair more than 50% of waking hours
4	Completely disabled. Cannot carry on any self-care. Totally confined to bed or chair
5	Dead

Appendix 4. Modified International Workshop on Chronic Lymphocytic Leukemia Criteria for Response Assessment

The determination of CLL response and progression will be based on standardized International Workshop on CLL (IWCLL) criteria {Hallek 2008}, as specifically modified for this study to reflect current recommendations which consider the study design and mechanism of action of idelalisib and similar drugs {Cheson 2012}.

1.1. Identification and Follow-up of Lesions and Organomegaly

CT/MRI scans are no longer required as of Amendment 4. The following guidelines are recommendations for local imaging studies, if done.

1.1.1. Index Lesions

For subjects entering the study with lymphadenopathy, up to 6 lymph nodes should be selected as index lesions that will be used to quantitate the status of the disease during study treatment. Ideally, the index lesions should be located in disparate regions of the body. Only peripheral nodes need be selected as index lesions, however, it is optimal if mediastinal and retroperitoneal areas of disease are assessed whenever these sites are involved.

Index lesions will be measured and recorded at baseline and at the stipulated intervals. The cross-sectional dimensions (the largest cross-sectional diameter, ie, the longest diameter (LD) × the longest perpendicular diameter (LPD) will be recorded for each index lesion. The product of the perpendicular diameters (PPD) for each index lesion and the shortest perpendicular diameter (SPD) for all index lesions will be calculated and recorded. The baseline SPD will be used as references by which objective disease response will be characterized during treatment. The nadir LD of individual lesions and the nadir SPD will be used as references by which CLL progression will be characterized. All LD and LPD diameters will be reported in cm and all PPDs and SPDs will be reported in cm².

A nodal mass may be selected as a nodal index lesion if it is both abnormal and measurable at baseline. A lymph node lesion is considered abnormal if it has a single diameter that is > 1.5 cm and is considered measurable if it has 2 perpendicular diameters that can be accurately measured in cross section with the LD being ≥1.0 cm and the LPD also being ≥1.0 cm.

At follow-up time points, the LDs for individual lesions and the SPD of all nodal index lesions will be considered. Because nodal index lesions that have 1 or both diameters > 0 cm and < 1.0 cm cannot be reliably measured, a default value of 1.0 cm will be assigned for each diameter that meets these criteria and the resulting PPD will be used in SPD calculations.

A new node that measures > 1.5 cm in the LD and > 1.0 cm in the LPD will be considered PD.

In cases in which a large lymph node mass has split into multiple components, all subcomponents regardless of size will be used in calculating the SPD. Progression of the lesion will be based on the SPD of sub-components. Lesion sub-components will have the true PPDs calculated. Similarly, lesion sub-components that are visible but neither abnormal nor measurable will have the default PPD of 1.0 cm² (1.0 cm × 1.0 cm) used in calculating the SPD.

If lesions merge, a boundary between the lesions may be established so the LD of each individual lesion can continue to be measured. If the lesions have merged in a way that they can no longer be separated by this boundary, the newly merged lesion will be measured bi-dimensionally.

1.1.2. Spleen and Liver

Both the spleen and liver will be assessed by CT/MRI scan at baseline and at the stipulated intervals during the study. The baseline and nadir values for the longest vertical dimension (LVD) of each organ will be used as reference to further characterize the objective tumor response of the measurable dimensions of the CLL during the study.

The spleen will be considered enlarged if it is > 12 cm in LVD {[Asghar 2011](#), [Bezerra 2005](#)}, with the LVD being obtained by multiplying the number of sections on which the spleen is visualized by the thickness of the sections (eg, if the spleen is seen in 14 contiguous cross-sectional images with 0.5-cm thickness, the LVD is recorded as 7 cm). The amount of enlargement of a spleen with LVD > 12 cm is equal to the LVD minus 12 cm. For subjects with splenomegaly at baseline evaluations of the spleen will consider only changes relative to the amount of enlargement at baseline. Splenic progression will be based on increase from the nadir measurement, or 12 cm if the nadir is ≤ 12 cm.

A 50% decrease (minimum 2 cm decrease) from baseline in the enlargement of the spleen or decrease in LVD to ≤ 12 cm by imaging is required for declaration of a splenomegaly response. Conversely, an increase in splenic enlargement by $\geq 50\%$ from nadir (minimum increase of 2 cm) is required for declaration of splenic progression; the spleen must be at least 14 cm in LVD to assess splenic progression.

The liver will be considered enlarged if it is > 18 cm in LVD {[Erturk 2006](#)}, with the LVD being obtained by multiplying the number of sections on which the liver is visualized by the thickness of the sections (eg, if the liver is seen in 36 contiguous cross-sectional images with 0.5-cm thickness, the LVD is recorded as 18 cm). The amount of enlargement of a liver with LVD > 18 cm is equal to the LVD minus 18 cm.

A 50% decrease (minimum 2 cm decrease) from baseline in the enlargement of the liver or decrease in LVD to ≤ 18 cm by imaging is required for declaration of a hepatomegaly response. Conversely, an increase in liver enlargement by $\geq 50\%$ from nadir (minimum increase of 2 cm) is required for declaration of hepatic progression; the liver must be at least 20 cm in LVD to assess hepatic progression.

1.1.3. Non-Index Lesions

Any other measurable and abnormal nodal lesions not selected for quantitation as index lesions may be considered non-index lesions. In addition, non-measurable evidence of CLL such as nodal lesions with both diameters < 1.0 cm, extra-nodal lesions, bone lesions, leptomenigeal disease, ascites, pleural or pericardial effusions, lymphangitis of the skin or lung, abdominal masses that are not confirmed and followed by imaging techniques, cystic lesions, previously irradiated lesions, lesions with artifacts may be considered as non-index disease.

The presence or absence of non-index disease should be recorded at baseline and at the stipulated intervals during the study. If present at baseline, up to 6 non-index lesions should be recorded. The non-index disease at baseline will be used as a general reference to further characterize regression or progression of CLL during assessments of the objective disease response during treatment. Measurements are not required and these lesions should be followed as “present”, “progressed” or “absent”.

1.2. Definitions of Disease Response and Progression

Responses will be categorized by the IRC as CR, CR with incomplete marrow recovery (CRi), PR, SD, or PD. In addition, a response category of not evaluable (NE) is provided for situations in which there is inadequate information to otherwise categorize response status. A response category of no disease (ND) is included for situations in which there is no evidence of tumor either at baseline or on the study.

The best OR will be determined. The best OR is the best response recorded from the start of treatment until progressive disease/recurrence (taking as reference for PD the smallest measurements recorded since treatment started). Subjects with NE or ND will be included in the denominator in the analyses of disease response.

1.2.1. Complete Response

To satisfy criteria for a CR, all of the following criteria must be met:

- No evidence of new disease
- ALC in peripheral blood of $<4 \times 10^9/L$
- Regression of all index nodal masses to normal size ≤ 1.5 cm in the LD
- Normal spleen and liver size
- Regression to normal of all nodal non-index disease and disappearance of all detectable non-nodal, non-index disease
- Morphologically negative bone marrow defined as $<30\%$ of nucleated cells being lymphoid cells and no lymphoid nodules in a bone marrow sample that is normocellular for age
- Peripheral blood counts meeting all of the following criteria:
 - ANC $> 1.5 \times 10^9/L$ without need for exogenous growth factors (eg, G-CSF)
 - Platelet count $\geq 100 \times 10^9/L$ without need for exogenous growth factors or transfusions
 - Hemoglobin ≥ 110 g/L (11.0 g/dL) without red blood cell transfusions or need for exogenous growth factors (eg, erythropoietin)

1.2.2 Partial Response

Subjects who fulfill all the criteria for a CR (including bone marrow criteria) but who have a persistent anemia, thrombocytopenia, or neutropenia or a hypocellular bone marrow that is related to prior or ongoing drug toxicity (and not to CLL) will be considered a CRi. 1.2.2. Partial Response

To satisfy criteria for a PR, all of the following criteria must be met:

- No evidence of new disease
- No index, splenic, liver, or non-index disease with worsening that meets the criteria for definitive PD
- Peripheral blood counts meeting ≥ 1 of the following criteria:
 - a) ANC $> 1.5 \times 10^9/L$ or $\geq 50\%$ increase over baseline without need for exogenous growth factors (eg, G-CSF)
 - b) Platelet count $\geq 100 \times 10^9/L$ or $\geq 50\%$ increase over baseline without need for exogenous growth factors or transfusions
 - c) Hemoglobin ≥ 110 g/L (11.0 g/dL) or $\geq 50\%$ increase over baseline without red blood cell transfusions or need for exogenous growth factors (eg, erythropoietin)
- Change in disease status meeting the following criteria:

Phase 1b:

- Subjects entering the study with baseline lymphocytosis, but without lymphadenopathy, hepatomegaly, or splenomegaly:
 - A decrease in peripheral blood ALC by $\geq 50\%$ from baseline or a decrease to $< 4 \times 10^9/L$.
- Subjects entering the study with baseline lymphocytosis AND ONLY ONE of the following additional abnormal baseline findings: baseline lymphadenopathy OR baseline hepatomegaly OR baseline splenomegaly:
 - In a subject with baseline lymphadenopathy, decrease by $\geq 50\%$ from the baseline in the SPD of the index nodal lesions
 - In a subject with enlargement of the spleen at baseline, a splenomegaly response as defined in Appendix 4 Section 1.1.2
 - In a subject with enlargement of the liver at baseline, a hepatomegaly response as defined in Appendix 4 Section 1.1.2
 - WITH OR WITHOUT a decrease in peripheral blood ALC by $\geq 50\%$ from baseline or a decrease to $< 4 \times 10^9/L$.

- Subjects entering the study with baseline lymphocytosis and AT LEAST TWO of the following additional abnormal baseline findings: baseline lymphadenopathy OR baseline hepatomegaly OR baseline splenomegaly:
 - Response demonstrated in AT LEAST TWO of the same additional abnormal baseline findings
 - OR response demonstrated in ONE of the same additional abnormal baseline findings AND a decrease in peripheral blood ALC by $\geq 50\%$ from baseline or a decrease to $< 4 \times 10^9/L$

Phase 2:

- Subjects entering the study with at least one lymph node with LD ≥ 20 mm and LPD of ≥ 10 mm at baseline:
 - Change in disease status meeting ≥ 2 of the following criteria, with 2 exceptions in which only 1 criterion is needed: (1) Only lymphadenopathy is present at baseline; (2) Only lymphadenopathy and lymphocytosis are present at baseline. In these 2 cases, only lymphadenopathy must improve to the extent specified below:
 - In a subject with baseline lymphocytosis ($ALC \geq 4 \times 10^9/L$), a decrease in peripheral blood ALC by $\geq 50\%$ from baseline or a decrease to $< 4 \times 10^9/L$
 - A decrease by $\geq 50\%$ from the baseline in the SPD of the index nodal lesions
 - In a subject with enlargement of the spleen at baseline, a splenomegaly response as defined in Appendix 4 Section 1.1.2.
 - In a subject with enlargement of the liver at baseline, a hepatomegaly response as defined in Appendix 4 Section 1.1.2
 - A decrease by $\geq 50\%$ from baseline in the CLL marrow infiltrate or in B-lymphoid nodules
- Subjects entering the study without lymphadenopathy but with quantifiable CLL in bone marrow at baseline:
 - Change in disease status meeting ≥ 2 of the following criteria, with 2 exceptions in which only 1 criterion is needed: (1) Only quantifiable CLL in bone marrow is present at baseline; (2) Only quantifiable CLL in bone marrow and lymphocytosis are present at baseline. In these 2 cases, only quantifiable CLL in bone marrow must improve to the extent specified below:
 - In a subject with baseline lymphocytosis ($ALC \geq 4 \times 10^9/L$), a decrease in peripheral blood ALC by $\geq 50\%$ from baseline or a decrease to $< 4 \times 10^9/L$
 - In a subject with enlargement of the spleen at baseline, a splenomegaly response as defined in Appendix 4 Section 1.1.2.

- In a subject with enlargement of the liver at baseline, a hepatomegaly response as defined in Appendix 4 Section 1.1.2
- A decrease by $\geq 50\%$ from baseline in the CLL marrow infiltrate or in B-lymphoid nodules

1.2.3. Stable Disease

To satisfy criteria for SD, the following criteria must be met:

- No evidence of new disease
- There is neither sufficient evidence of tumor shrinkage to qualify for PR nor sufficient evidence of tumor growth to qualify for definitive PD

1.2.4. Definitive Progressive Disease

The occurrence of any of the following events indicates definitive PD:

- Evidence of any new disease:
 - a) A new node that measures >1.5 cm in the LD and >1.0 cm in the LPD
 - b) New or recurrent splenomegaly, with a minimum LVD of 14 cm
 - c) New or recurrent hepatomegaly, with a minimum LVD of 20 cm
 - d) Unequivocal reappearance of an extra-nodal lesion that had resolved
 - e) A new unequivocal extra-nodal lesion of any size
 - f) New non-index disease (eg, effusions, ascites, or other organ abnormalities related to CLL)

Isolated new effusions, ascites, or other organ abnormalities are not sufficient evidence alone of PD unless histologically confirmed. Thus, a declaration of PD should not be made if this is the only manifestation of apparently new disease.

- Evidence of worsening of index lesions, spleen or liver, or non-index disease:
 - a) Increase from the nadir by $\geq 50\%$ in the SPD of index lesions
 - b) Increase from the nadir by $\geq 50\%$ in the LD if an individual node that now has an LD of >1.5 cm and an LPD of > 1.0 cm
 - c) Splenic progression defined as an increase in splenic enlargement by $\geq 50\%$ from nadir (with a minimum 2 cm increase and a minimum LVD of 14 cm)
 - d) Hepatic progression defined as an increase in hepatic enlargement by $\geq 50\%$ from nadir (with a minimum 2 cm increase and minimum LVD of 20 cm)

- e) Unequivocal increase in the size of non-index disease (eg, effusions, ascites, or other organ abnormalities related to CLL)
- f) Transformation to a more aggressive histology (eg, Richter syndrome) as established by lymph node biopsy or other tissue biopsy, or fluid cytology (with the biopsy or fluid cytology date being considered the date of CLL progression if the subject has no earlier objective documentation of CLL progression).
- Decrease in platelet count or hemoglobin that is attributable to CLL, is not attributable to an autoimmune phenomenon, and is confirmed by bone marrow biopsy showing an infiltrate of clonal CLL cells:
 - a) The current platelet count is $< 100 \times 10^9/L$ and there has been a decrease by $> 50\%$ from the highest on-study platelet count
 - b) The current hemoglobin is $< 110 \text{ g/L}$ (11.0 g/dL) and there has been a decrease by $> 20 \text{ g/L}$ (2 g/dL) from the highest on-study hemoglobin
- At any time greater than 4 weeks after the discontinuation of idelalisib: an increase in the number of blood lymphocytes by 50% or more with at least 5000 B lymphocytes per microliter as measured from the nadir during that time period.

1.2.5. Non-Evaluable and No Disease

In a subject who does not have evidence of PD, the occurrence of any of the following conditions indicates a response status of NE:

- There are no images or inadequate or missing images.
- Images of the liver and/or spleen are missing at that time point (with the exception that absence of splenic images will not result in an NE designation in a subject known to have undergone splenectomy).

A time-point will be considered to have a response of NE if any index lesion is missing. PD may be assigned at any time point regardless of the extent of missing index or non-index lesions. Missing non-index lesions will not impact the ability to assess for response or disease progression.

No Disease Subjects have a status of ND if all of the following conditions occur:

- No index disease noted at baseline or on-the study
- No non-index disease noted at baseline or on-the study
- No enlargement of the liver or spleen at baseline or on-the study
- No abnormalities of peripheral blood counts (elevated ALC or abnormally low ANC, platelet count, or hemoglobin) and no evidence of CLL in bone marrow (if available) at baseline or on the study

1.3. Lymphocytosis During Therapy

Idelalisib can mobilize CLL cells from tissues into the peripheral blood. This characteristic pharmacological action can be prominent early in therapy but can persist over time and should not be confused with disease progression in subjects who have persistent control of other CLL-related signs and symptoms.

In the absence of other objective evidence of disease progression, the occurrence of lymphocytosis will not preclude subjects from meeting the criteria for a PR if other criteria for PR are met and will not be considered evidence of CLL progression if occurring in isolation.

Subjects with lymphocytosis should be continued on study drug until the occurrence of definitive disease progression (ie, disease progression that is manifest by worsening CLL-related signs other than lymphocytosis alone), or the occurrence of another reason to discontinue study treatment as described in Protocol Section 6.

Appendix 5. Pregnancy Precautions, Definition for Female of Childbearing Potential, and Contraceptive Requirements

1) Definitions

a. Definition of Childbearing Potential

For the purposes of this study, a female born subject is considered of childbearing potential following the initiation of puberty (Tanner stage 2) until becoming post-menopausal, unless permanently sterile or with medically documented ovarian failure.

Women are considered to be in a postmenopausal state when they are ≥ 54 years of age with cessation of previously occurring menses for ≥ 12 months without an alternative cause. In addition, women of any age with amenorrhea of ≥ 12 months may also be considered postmenopausal if their follicle stimulating hormone (FSH) level is in the postmenopausal range and they are not using hormonal contraception or hormonal replacement therapy.

Permanent sterilization includes hysterectomy, bilateral oophorectomy, or bilateral salpingectomy in a female subject of any age.

b. Definition of Male Fertility

For the purposes of this study, a male born subject is considered of fertile after the initiation of puberty unless permanently sterile by bilateral orchidectomy or medical documentation.

2) Contraception Requirements for Female Subjects

a. Study Drug Effects on Pregnancy and Hormonal Contraception

Idelalisib is contraindicated in pregnancy as a malformation effect has been demonstrated/suspected or is unknown, taking into consideration class effects, genotoxic potential, or a strong suspicion of human teratogenicity/fetotoxicity in early pregnancy based on non-clinical data. Idelalisib has demonstrated/suspected or has insufficient data to exclude the possibility of a clinically relevant interaction with hormonal contraception that results in reduced contraception efficacy. Therefore, contraceptive steroids are not recommended as a contraceptive method either solely or as a part of a contraceptive regimen. Please refer to the latest version of the IB for additional information.

b. Contraception Requirements for Female Subjects of Childbearing Potential

The inclusion of female subjects of childbearing potential requires the use of highly effective contraceptive measures. They must also not rely on hormone-containing contraceptives as a form of birth control during the study. They must have a negative serum pregnancy test at Screening and a negative pregnancy test on the Baseline/Day 1 visit prior to randomization. Pregnancy tests will be performed at monthly intervals thereafter. Female subjects must agree to one of the following from the Screening visit throughout the study, and for 30 days from the last dose of idelalisib or 12 months from the last dose of BI 836826 (whichever is later).

- Complete abstinence from intercourse of reproductive potential. Abstinence is an acceptable method of contraception only when it is in line with the subject's preferred and usual lifestyle.

Or

- Consistent and correct use of 1 of the following methods of birth control listed below.
 - Intrauterine device (IUD) with a failure rate of <1% per year
 - Tubal sterilization
 - Essure micro-insert system (provided confirmation of success 3 months after procedure)
 - Vasectomy in the male partner (provided that the partner is the sole sexual partner and had confirmation of surgical success 3 months after procedure)

Female subjects must also refrain from egg donation and in vitro fertilization during treatment and for 30 days from the last dose of idelalisib or 12 months from the last dose of BI 836826 (whichever is later).

3) Contraception Requirements for Male Subjects

It is theoretically possible that a relevant systemic concentration may be achieved in a female partner from exposure of the male subject's seminal fluid. Therefore, male subjects with female partners of childbearing potential must use condoms during treatment and until 90 days following the last dose of idelalisib or 12 months from the last dose of BI 836826 (whichever is later). Additional contraception recommendations should also be considered if the female partner is not pregnant.

Male subjects must also refrain from sperm donation during treatment and until at least 90 days following the last dose of idelalisib or 12 months from the last dose of BI 836826 (whichever is later).

Unacceptable Birth Control Methods

Birth control methods that are unacceptable include periodic abstinence (eg, calendar, ovulation, symptothermal, post-ovulation methods), withdrawal (coitus interruptus), spermicides only, and lactational amenorrhea method (LAM). Female condom and male condom should not be used together.

4) Procedures to be Followed in the Event of Pregnancy

Subjects will be instructed to notify the investigator if they become pregnant at any time during the study, or if they become pregnant within 30 days for females or 90 days for female partners of male subjects of last study drug dose. Subjects who become pregnant or who suspect that they are pregnant during the study must report the information to the investigator and discontinue study drug immediately. Subjects whose partner has become pregnant or suspects she is pregnant during the study must report the information to the investigator. Instructions for reporting pregnancy, partner pregnancy, and pregnancy outcome are outlined in Section 7.7.2.1.

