- 10) For male subjects of reproductive potential a willingness to both: 1) use a protocol-recommended method of contraception, when having intercourse with females of child bearing potential, and 2) to refrain from sperm donation, from enrollment (Day 1) throughout the study and for 90 days following the last dose of idelalisib or 12 months from the last dose of BI 836826 (whichever is later).
- 11) In the judgment of the investigator, participation in the protocol offers an acceptable benefit-to-risk ratio when considering current CLL disease status, medical condition, and the potential benefits and risks of alternative treatments for CLL.
- 12) Willingness and ability to comply with scheduled visits, drug administration plan, imaging studies, laboratory tests, other study procedures, and study restrictions, including mandatory prophylaxis for PJP.

- 13) Evidence of a personally signed informed consent indicating that the subject is aware of the neoplastic nature of the disease and has been informed of the procedures to be followed, the experimental nature of the therapy, alternatives, potential benefits, possible side effects, potential risks and discomforts, and other pertinent aspects of study participation.

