7.7.2. Instructions for Reporting Special Situations

7.7.2.1. Instructions for Reporting Pregnancies

The investigator should report pregnancies in female study subjects that are identified after initiation of study medication and throughout the study, including the post study drug follow-up period, to Gilead DSPH using the pregnancy report form within 24 hours of becoming aware of the pregnancy.

Refer to the eCRF completion guidelines for full instructions on the mechanism of pregnancy reporting.

The pregnancy itself is not considered an AE nor is an induced elective abortion to terminate a pregnancy without medical reasons.

Any premature termination of pregnancy (eg, a spontaneous abortion, an induced therapeutic abortion due to complications or other medical reasons) must be reported within 24 hours as an SAE. The underlying medical reason for this procedure should be recorded as the AE term.

A spontaneous abortion is always considered to be an SAE and will be reported as described in Sections 7.1.1 and 7.1.2. Furthermore, any SAE occurring as an adverse pregnancy outcome post study must be reported to Gilead DSPH.

The subject should receive appropriate monitoring and care until the conclusion of the pregnancy. The outcome should be reported to Gilead DSPH using the pregnancy outcome report form. If the end of the pregnancy occurs after the study has been completed, the outcome should be reported directly to Gilead DSPH. Gilead DSPH contact information is as follows:

Email: PPD or Fax: PPD

Pregnancies of female partners of male study subjects exposed to idelalisib or BI 836826 must also be reported and relevant information should be submitted to Gilead DSPH using the pregnancy and pregnancy outcome forms within 24 hours. Monitoring of the subject should continue until the conclusion of the pregnancy. If the end of the pregnancy occurs after the study has been completed, the outcome should be reported directly to Gilead DSPH. Gilead DSPH contact information is as follows: Email: PPD or Fax: PPD .

Refer to [Appendix 5](#) for Pregnancy Precautions, Definition for Female of Childbearing Potential, and Contraceptive Requirements.

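### The pregnancy notification window in Appendix 5 omits the 12 months after BI 836826 during which contraception is still required

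*Protocol*

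**What the plan says.** **Notification by the subject.** Protocol Appendix 5, item 4, asks subjects to tell the investigator of a pregnancy while they are on study and, beyond that, "if they become pregnant within 30 days for females or 90 days for female partners of male subjects of last study drug dose".

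**Contraception.** For female subjects, Appendix 5 item 2b and inclusion criterion 9 (Section 4.2) require contraception throughout the study and then "for 30 days from the last dose of idelalisib or 12 months from the last dose of BI 836826 (whichever is later"). For male subjects, Appendix 5 item 3 requires condoms "until 90 days following the last dose of idelalisib or 12 months from the last dose of BI 836826 (whichever is later"), and inclusion criterion 10 sets the same period: "for 90 days following the last dose of idelalisib or 12 months from the last dose of BI 836826 (whichever is later").

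**Reporting by the investigator (Section 7.7.2.1).**
- For female subjects the duty covers "pregnancies in female study subjects that are identified after initiation of study medication and throughout the study, including the post study drug follow-up period". The length of that follow-up period is not given.
- For partners there is no time limit: "Pregnancies of female partners of male study subjects exposed to idelalisib or BI 836826 must also be reported".
- On outcomes, "A spontaneous abortion is always considered to be an SAE", and "any SAE occurring as an adverse pregnancy outcome post study must be reported".
- The same section says that a pregnancy is not in itself an adverse event.

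**Other relevant text.** Section 6.6.2 has known pregnancies followed to their end after a subject discontinues. Section 6.7 places the last visit 30 days after the final BI 836826 dose, at Week 50 at the latest. Section 7.3.2 collects adverse events to 30 days after the last dose of either drug. Section 7.3.3 releases investigators from actively looking for SAEs after the 30-day follow-up.

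**The concern.** Item 4 uses 30 and 90 days, which are the idelalisib parts of the contraception rule, and leaves out the BI 836826 part. The protocol therefore tells a woman to avoid pregnancy for a year after her last infusion, but for most of that year it does not ask her to say if she becomes pregnant.

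Once subjects leave at about Week 50, their own report is the main way such a pregnancy would become known. If the text is followed as written, a pregnancy inside the protocol's own precautionary window could go unrecorded. The SAE rules are only a partial backstop: they need an adverse outcome, and they depend on the investigator hearing of it.

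This is a matter of safety follow-up. No endpoint, listing or planned analysis depends on it.

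**Working it through.** **1. Inputs**
- Last BI 836826 infusion on schedule: Week 46, Day 316 (Appendix Table 1).
- Idelalisib continues 4 weeks after the final infusion, through Week 50 (Section 6.5). That is Day 344 (316 + 28), the day given for the end-of-study visit in Appendix Table 2.
- Latest permitted infusion: Week 48 (Section 5.4.2), taken as Day 316 + 14 = Day 330.
- Assumption: 12 months = 365 days.

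**2. Formula for female subjects.** Let k ≥ 0 be the days from the last BI 836826 dose to the last idelalisib dose. Count from the last BI 836826 dose, and read item 4's last dose as the later of the two drugs.
- Item 4 notification ends at k + 30.
- Contraception ends at the later of k + 30 and 365.
- Uncovered days of conception = 365 − (k + 30) = 335 − k, and never below 0.

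**3. Results**

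| Situation | k | Uncovered days | Share of 365 |
|---|---|---|---|
| On schedule: Day 316, idelalisib to Day 344 | 28 | 307 | 84% |
| Last infusion Day 330, idelalisib to Day 344 | 14 | 321 | 88% |
| Both drugs stopped the same day | 0 | 335 | 92% |
| BI 836826 held after Week 38 (Day 260), idelalisib to Day 344 | 84 | 251 | 69% |
| BI 836826 held after Week 26 (Day 176), idelalisib to Day 344 | 168 | 167 | 46% |

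Check of the first row by study day: notification ends on Day 344 + 30 = 374, contraception ends on Day 316 + 365 = 681, and 681 − 374 = 307.

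The same-day case follows Section 5.6, which stops both drugs when either is permanently discontinued during combination therapy. The two hold cases are possible because Section 5.4.2 sets no limit on the length of a hold. The gap closes only when k ≥ 335, which idelalisib to Week 50 does not allow on the schedule above.

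**4. Does other text fill the gap?**
- *Section 7.7.2.1, female subjects.* The duty runs through the study and includes the follow-up period, so it ends when she leaves. Thirty days is inferred from Sections 6.7, 7.3.2 and 7.3.3. This sentence also counts when a pregnancy is identified, whereas item 4 counts when it begins.
- *Section 7.7.2.1, outcomes.* Spontaneous abortions, medically indicated terminations and SAE outcomes are covered. An uncomplicated pregnancy is not, because it is not an adverse event.
- *Section 6.6.2.* It follows a known pregnancy to its end. It creates no duty to notify one that begins later.
- *Partners.* Item 4 is also short here, by 365 − 90 − 28 = 247 days on schedule. The investigator's reporting duty has no time limit, however, so the shortfall lies only in what the male subject is told.

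What remains is the uncomplicated pregnancy of a female subject that begins after she leaves the study and after item 4's 30 days.

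**The case against.** **Section 7.7.1** treats pregnancy reports as special situations whether or not an adverse event occurs, and describes the form as used for pregnancies in female subjects and in partners of men on study. The on-study qualifier could be read as applying only to the men, which would leave female subjects without a time limit. The wording is ambiguous, but it describes what a form is for. It does not tell a subject to notify anyone after she has left.

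**The follow-up period in Section 7.7.2.1 is undefined**, and longer periods appear elsewhere: the synopsis has annual survival collection for 5 years after End of Study, and Section 5.7.11 has hepatitis B monitoring for a year after BI 836826. The survival collection falls after End of Study and carries no pregnancy duty. The hepatitis B monitoring applies only during study participation. It stands that 30 days is an inference, but the reporting sentence ends with the study in any case.

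**Unseen documents.** The consent form and the eCRF completion guidelines may set a longer period. This stands, and the finding is limited to the visible protocol.

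**Exposure and proportion.** The protocol gives no BI 836826 half-life and no reproductive toxicity finding for it, so exposure throughout the 12 months is not shown. The day counts measure calendar time and not risk, and CLL is largely a disease of older people (Section 1.1.1 gives a median age of 72 years at diagnosis). All of this stands and keeps the point minor. It does not explain why notification should be shorter than the contraception period that the protocol itself chose.

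**Conclusion.** The point holds. Item 4 is shorter than the contraception rule it accompanies, and no visible text covers the remaining case for female subjects. The uncovered interval is 335 − k days: 307 days (84% of the year) on schedule, up to 335 days (92%) if both drugs stop together, and less if BI 836826 is held while idelalisib continues.

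This rests on three assumptions: 12 months is 365 days, the last dose in item 4 means the later of the two drugs, and the unseen documents do not already set a longer period. The mismatch in wording is certain. Its practical effect is small and may be nil, because only two subjects are enrolled and the documents do not give their sex or reproductive potential. It is a minor defect in safety follow-up, with no bearing on the analysis.

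**What to change.** - **Appendix 5, item 4:** require notification of any pregnancy that begins during the study, or up to the later of two dates: 30 days (female subjects) or 90 days (female partners) after the last idelalisib dose, and 12 months after the last BI 836826 dose.
- **Section 7.7.2.1, first paragraph:** extend the female-subject duty to pregnancies that begin up to that same date, whenever they are identified. Leave the partner sentence without a time limit.
- **Enrolled subjects:** inform the two subjects as applicable.

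On schedule, this moves the end of notification for female subjects from Day 374 to Day 681 and closes the gap.

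The cost is two sentences in an amendment with documented IRB/IEC approval (Section 9.2.1), a possible consent-form update, and contact with the subjects concerned. It uses the subject-to-investigator route that item 4 already relies on and adds no visits or tests. If neither subject nor a partner could become pregnant, the sponsor could document that instead.
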